## Study Protocol and Statistical Analysis Plan

### **Participants and setting**

Participants included 20 high-risk parent-infant dyads hospitalized in an urban, level IV NICU. Consecutively eligible dyads from May 2023 to April 2024 were recruited if the infant was hospitalized in the NICU for > 7 days; received a referral for post-NICU physical therapy, occupational therapy, and/or speech-language pathology (or for the state-wide early intervention program) at NICU discharge; was referred to the Baby Bridge program at least 48 hours before NICU discharge; had a chronological age of < 6 months at the time of NICU discharge; and were from a family who spoke English. Infants who lived any distance away from the hospital were enrolled; however, infants who were not going to reside in the state of California following NICU discharge were excluded. Infants were deemed 'high-risk' for developmental challenges if they were recommended by the NICU medical team for therapy. Although we acknowledge that the term "high risk" can refer to high risk of medical complications or high risk of cerebral palsy, we use the term "high risk" to define the infant's need for therapeutic interventions across a multitude of constructs including for language, cognition, self-regulation, sensory, motor, and feeding. A member of the research team attended weekly discharge rounds and reviewed the electronic medical record. Within discharge rounds, communication between the medical team and research team occurred, and the medical team referred infants to the Baby Bridge program through an online referral process in REDCap. The research team then screened and recruited those who were eligible.

Enrolled infants and families were randomized to receive Baby Bridge services either through telehealth or in-person visits. Parent-infant dyads were enrolled at least 2 days before NICU discharge to enable rapport to be established (between the Baby Bridge therapist and family) through a visit to the NICU when possible and via telephone, text or email messaging when an in-person visit was not possible prior to discharge. This first contact was attempted to be in-person in the NICU for both the telehealth and in-person groups. Enrolled infants and families then had a Baby Bridge telehealth or in-person visit scheduled within one week of discharge (depending on their group assignment). Subsequent individual weekly visits were adapted to in-person or telehealth (varying from assigned group) when needed or deemed appropriate (requested by the family or therapist or when an in-person visit was felt to improve the quality of the therapy session). Weekly Baby Bridge programming was conducted until other therapy through the state-wide early intervention program commenced, as in the infant was receiving therapy services as recommended. We also tracked rates of enrollment, rates and reasons for any cancellations, and completion of the program (defined as being seen until community-based early intervention services commenced). Infants were withdrawn if they were transferred to another hospital or if they were readmitted to the hospital and additional contact was not possible or feasible.

### **Sociodemographic and medical data**

Sociodemographic and medical data were collected from the electronic medical record for each dyad enrolled to better understand differences between groups as well as to define sample characteristics. Sociodemographic factors collected included: infant

race, insurance type (public or private), maternal age, number of siblings, home distance from the hospital, and categorization of home residence (urban with <3,000 people per square mile, suburban with between 1,000 and 3,000 people per square mile, or rural with <1,000 people per square mile). Medical factors collected included: estimated gestational age at birth, the primary condition of the infant (congenital anomaly, preterm birth, or neurological condition not related to preterm birth or congenital anomaly), number of days of endotracheal intubation, number of days of hospitalization, and whether or not the infant was orally feeding at time of hospital discharge.

### **In-person group assignment**

For those assigned to the in-person Baby Bridge group, the first visit was scheduled in the home within one week of NICU discharge, and attempts were made to see the infant weekly in the home environment for a one-hour therapy session. Scheduled visits were confirmed with families via text messaging the day before each visit. Visits were rescheduled to telehealth in the event of therapist illness, parent preference or parent/child illness, or distance or therapist schedule limitations. Changes of visits from in-person to telehealth were tracked along with their reasoning.

### **Telehealth group assignment**

For those assigned to the telehealth Baby Bridge group, a first telehealth visit was scheduled within one week of discharge, and weekly telehealth visits were scheduled thereafter. However, parents were informed that in-person visits were an option when needs arise. Adaptations from a telehealth visit to an in-person visit were made in the event of therapist clinical judgment due to the medical complexity or feeding/tonal abnormalities of

the infant and parent preference or rapport building. Visit adaptations were tracked along with the reasoning for them.

### **Implementation outcomes**

We defined measures for this study based on previous implementation research (Lewis et al., 2015; Proctor et al., 2011; Proctor et al., 2009). The primary outcome of interest for this study was cost difference between telehealth and in-person visits of the Baby Bridge program. We also investigated implementation outcomes of adoptability, feasibility, adaptations, and acceptability. Many of the procedures here mirror a previous article on feasibility, which enrolled a different sample to assess the same outcomes in context of telehealth only, whereas this manuscript enables exploration of the differences when comparing to an in-person model.

### **Cost**

Cost is an important factor when determining feasibility of an intervention. When resources are limited, it can aid in choosing one intervention over another. For the purposes of this project, we estimated costs associated with each Baby Bridge visit. We did not assess cost across group assignment, due to the allowed adaptations to each visit type. Cost was defined in relation to the organizational cost of providing Baby Bridge visits and included the time that the therapist spent conducting therapy sessions (billable time), administrative time (documentation, communication with families), driving (for in-person visits), and mileage reimbursement. The total billable and non-billable time that the therapist spent (including therapy session time, administrative time, and drive time) was

multiplied by \$50 per hour, an hourly wage that matches typical rates across the United States and in California (29-1122 *Occupational Therapists*, 2024). Mileage reimbursement was calculated at the \$.67 per mile, the California mileage reimbursement rate for employees (2024 *Updated Mileage Reimbursement Rates for Use of Personal Vehicle and Private Aircraf*, 2024). Further, the number of billable minutes (in evaluation, for therapeutic activities, or therapeutic exercises) were put in context of Current Procedural Terminology (CPT)/Healthcare Common Procedure Coding System (HCPCS) codes and reimbursement amounts for Fee For Service Medi-Cal (California Medicaid) (though we acknowledge this reimbursement rate could differ drastically depending on actual insurance type). This enabled a total amount of reimbursable potential in context of the total cost of programming, with the ability to explore differences across telehealth and in person costs. Because many infants had some adaptations to their assigned type of therapy visit, rather than investigating across assigned groups, we analyzed cost based on actual visit type (telehealth or in person) rather than assigned group type.

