## **Analysis**

A power analysis to determine sample size was not conducted, as this is a pilot study aimed at understanding initial differences across groups while determining variance to aid in future sample size determination for a larger trial. Sociodemographic and medical factors are reported descriptively and differences across groups were investigated using independent samples t-tests and chi-square analysis.

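### The primary cost comparison is by visit type as delivered, so randomisation does not protect it; a cost-per-dyad summary by arm and a specified regression would be a cheap improvement

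*Combined protocol and SAP*

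**What the plan says.** The Participants and setting section describes a randomised design: "Enrolled infants and families were randomized to receive Baby Bridge services either through telehealth or in-person visits". Eligibility was not limited by distance within California: "Infants who lived any distance away from the hospital were enrolled".

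Implementation outcomes makes the primary outcome the cost difference between the two kinds of visit. The Cost subsection there says "We did not assess cost across group assignment, due to the allowed adaptations to each visit type", and again that "rather than investigating across assigned groups, we analyzed cost based on actual visit type (telehealth or in person) rather than assigned group type". Cost counts therapist time, including driving, at $50 per hour, plus mileage at $0.67 per mile. The Cost paragraph under Analysis plans a descriptive report, t-tests and linear regression by visit type. It names no covariates and no summary by arm.

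The In-person group assignment section states: "Visits were rescheduled to telehealth in the event of therapist illness, parent preference or parent/child illness, or distance or therapist schedule limitations". The Telehealth group assignment section allows moves the other way for clinical complexity, feeding or tone problems, parent preference and rapport; distance is not among those reasons. The Sociodemographic and medical data section records "home distance from the hospital". The Analysis section describes the pilot as "aimed at understanding initial differences across groups while determining variance to aid in future sample size determination for a larger trial".

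**The concern.** Two things follow from analysing cost only by the visit type delivered.

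First, the contrast is not the one that randomisation created. Which visits end up in person depends on choices made after allocation. One stated reason for those choices, distance, is itself a component of in-person cost. If the visits moved to telehealth are the ones with long drives, the remaining in-person visits are cheaper than in-person delivery to all enrolled families would be.

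Second, the pilot is meant to inform a larger trial. If that trial randomises dyads and compares cost by arm, it needs the SD of total cost per dyad. Per-visit SDs cannot supply it, because total cost per dyad also depends on the number of visits and on how alike visits are within a dyad.

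At stake is how the primary result is read and whether the pilot can size a cost comparison. Switching unrelated to cost, as illness may be, would not bias the per-visit means.

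**Working it through.** The plan gives no cost, distance or switching data and no power calculation, so there is no stated figure to reproduce. What follows is an illustration.

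**Inputs from the plan:** $50 per hour, $0.67 per mile, 20 dyads.

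**Assumed:** half of families at a 10-mile round trip and half at 60 miles; 35 mph; equal session and administrative time for both visit types; equal visit numbers per arm; 10 dyads per arm (the allocation ratio is not stated).

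**Step 1. Travel cost.** Per mile: 0.67 + 50/35 = $2.0986. Near visit: 10 × 2.0986 = $20.99. Far visit: 60 × 2.0986 = $125.91. Mean over all families: $73.45. With equal session and administrative time, this is the same-visit gap, that is, in person minus telehealth for all families.

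**Step 2. Distance-driven switching.** Half of the far visits in the in-person arm (25% of that arm's visits) move to telehealth.
- As delivered: (0.5 × 20.99 + 0.25 × 125.91)/0.75 = $55.96, which is 23.8% below $73.45.
- By arm: 0.5 × 20.99 + 0.25 × 125.91 = $41.97.

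**Step 3. Random switching of the same 25%.** As delivered: $73.45, no bias. By arm: 0.75 × 73.45 = $55.09. In Step 2 the by-arm gap therefore loses 73.45 − 55.09 = $18.36 to ordinary crossover dilution and 55.09 − 41.97 = $13.12 to distance selection.

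**Step 4. Add crossover the other way.** Suppose 20% of telehealth-arm visits also go in person, regardless of distance.
- As delivered: (0.75 × 55.96 + 0.2 × 73.45)/0.95 = $59.64, which is 18.8% below $73.45.
- By arm: 41.97 − 0.2 × 73.45 = $27.28.

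| Scenario | Same-visit gap | As delivered | By arm |
|---|---|---|---|
| 25% of in-person arm switched at random | $73.45 | $73.45 | $55.09 |
| Half of far in-person-arm visits switched | $73.45 | $55.96 | $41.97 |
| As above, plus 20% of telehealth arm in person | $73.45 | $59.64 | $27.28 |

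**Step 5. Sensitivity.** With switching from the in-person arm only, the percentage error is the mean miles of delivered in-person visits divided by the mean miles of all families, minus 1. Wage, speed and mileage rate cancel. With 10%, 25% or 50% of far visits switched it is −3.8%, −10.2% or −23.8% for 10/60 miles, and −1.8%, −4.8% or −11.1% for 20/40 miles. With a 10-mile near trip, far trips of 40 to 100 miles and 25% to 75% of far visits switched, it runs from about −9% to −49%.

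**Step 6. What distance in the regression would do.** Distance raises in-person cost only, so a main effect is not enough. With a visit-type-by-distance interaction, the gap at the mean distance of all families is 35 × 2.0986 = $73.45, which recovers the same-visit gap if home distance tracks miles driven.

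**Step 7. Precision of a by-arm summary.** The 95% CI half-width is t(0.975, 18) × √(2/10) = 0.94 SD with 10 per arm, and t(0.975, 14) × √(2/8) = 1.07 SD with 8 per arm. The 95% limits for a pooled SD on 18 df are 0.76 to 1.48 times its estimate.

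**The case against.** The strongest reply is that this is a disclosed choice of question. The primary outcome is defined per visit, the Cost section says twice that assigned group is not used and gives the reason, and the analysis section agrees. That stands. A reader might infer that the plan contradicts itself or mishandles its primary outcome; the documents do not support that.

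It can also be said that the by-arm figure is no better an estimate of the stated outcome. This stands too: in every illustration the as-delivered gap is nearer the same-visit gap than the by-arm gap is ($59.64 against $27.28, where the target is $73.45). Cost by arm answers a different question, the cost of each offer with its permitted adaptations, and belongs beside the per-visit result, not in its place.

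The pilot's stated aim does not mention cost, and feasibility, adaptations and acceptability are compared by arm. That weakens the point but does not remove it, since cost is the primary outcome and the aim is stated for the study as a whole. The planned proportion of visits delivered as assigned, combined with per-visit costs, would approximate mean cost per visit by arm. It would give no total per dyad, SD or CI.

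Finally, all the dollar figures rest on assumed distances and switching. That stands in full.

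**Conclusion.** A recommended improvement, not an error. It is certain from the text that no cost summary by randomised arm is planned and that the cost regression names no covariates. Adjustment for distance is therefore neither stated nor ruled out.

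The direction of distance-driven switching, taken alone, is clear: it lowers the as-delivered in-person mean relative to in-person delivery to all enrolled families. The net direction and size are not known. The In-person group assignment section lists several other reasons for switching, no counts are given, and moves to in-person for clinical complexity cannot be signed or sized from the documents.

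A reader might infer that the published cost gap is understated by roughly a quarter. The documents do not support that. The 23.8% figure is one assumed scenario in a set whose errors run from about 2% to 49%, and switching unrelated to distance would give none.

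**What to change.** 1. Keep the per-visit comparison and label it non-randomised.
2. Beside it, as a descriptive companion, report total cost per dyad by randomised arm, costing every visit in the modality delivered. Give the mean and SD in each arm, the difference and a dyad-level 95% CI (Welch or bootstrap).
3. Specify the cost regression as visit type, recorded home distance and their interaction, reporting the difference at the mean home distance of enrolled dyads. Cluster errors by dyad with a small-sample correction, because each dyad contributes repeated visits. Leave out medical covariates; 20 dyads will not carry them.
4. Tabulate switched visits by recorded reason.

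The cost is a few lines of text, one aggregation to dyad level, one model specification and one table, all from data the documents say were collected. There are downsides. Crossover dilutes the by-arm contrast, total cost also varies with when early intervention starts, and home distance is only a proxy for miles driven. The by-arm interval will also be wide, so the companion summary should be read as descriptive.

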## **Cost**

The cost of in-person visits vs. telehealth visits are reported descriptively. Differences in costs across telehealth and in-person visits were investigated using independent samples t-tests and linear regression models.

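### Only in-person visits carry travel cost, so the zero-difference test on total visit cost is nearly predetermined in sign; estimate the difference by component instead

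*Combined protocol and SAP*

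**What the plan says.** The combined protocol and SAP states under Implementation outcomes: "The primary outcome of interest for this study was cost difference between telehealth and in-person visits of the Baby Bridge program". The Cost section there defines organisational cost as session time plus "administrative time (documentation, communication with families), driving (for in-person visits), and mileage reimbursement". All therapist time, driving included, is priced at $50 per hour and mileage at $0.67 per mile. The comparison is by delivered visit type: "we analyzed cost based on actual visit type (telehealth or in person) rather than assigned group type".

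Under Analysis, the Cost section says "The cost of in-person visits vs. telehealth visits are reported descriptively", and then "Differences in costs across telehealth and in-person visits were investigated using independent samples t-tests and linear regression models". It names no component breakdown, regression covariates, confidence interval or allowance for repeated visits in the same dyad.

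Three other sections bear on this:

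- In-person group assignment lists distance among the reasons for moving a visit to telehealth.
- Telehealth group assignment allows a move to in-person for medical complexity, feeding or tone problems, parent preference or rapport.
- Sociodemographic and medical data records each enrolled dyad's home distance from the hospital.

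**The concern.** Two of the four cost components, driving and mileage, are zero for telehealth by definition and positive for every home visit. A test of equal total cost therefore starts from a null that only an offsetting excess of telehealth time could make true. A small p-value would mostly confirm that driving costs money, and would leave open whether telehealth changes session or administrative time. A large p-value would be just as ambiguous, since travel and extra telehealth time can cancel.

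Two consequences follow.

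- **Variance.** The Analysis section gives variance for a later trial as a purpose of the pilot. The spread of undivided in-person cost may largely describe where these 20 families live.
- **Selection.** If distant home visits are the ones converted, the mean travel cost of the visits that remain is lower than the cost of delivering the in-person programme to the enrolled families.

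**Working it through.** The documents give no cost, distance, visit-count or power figure, so there is nothing of the plan's own to reproduce.

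**Inputs from the Cost section:** $50 per hour for all time; $0.67 per mile; travel for in-person visits only. **Assumed:** distance, driving speed, visit counts, visit times and SDs.

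**Step 1. Travel cost and break-even.** For round-trip miles D at speed v, travel = 50 × D/v + 0.67 × D. Extra telehealth minutes that cancel it = travel/50 × 60. For D = 20 and v = 30: 33.33 + 13.40 = $46.73, and 46.73/50 × 60 = 56 minutes.

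| Round trip (miles) | Travel at 30 mph (45 to 20 mph) | Break-even minutes (45 to 20 mph) |
|---|---|---|
| 5 | $11.68 ($8.91 to $15.85) | 14 (11 to 19) |
| 10 | $23.37 ($17.81 to $31.70) | 28 (21 to 38) |
| 20 | $46.73 ($35.62 to $63.40) | 56 (43 to 76) |
| 40 | $93.47 ($71.24 to $126.80) | 112 (85 to 152) |

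The planned home session is one hour. From about 20 round-trip miles, telehealth would need roughly another session's worth of therapist time to cancel travel.

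**Step 2. What the test would do.** Simulated Welch t-tests, two-sided 0.05, 1,500 runs, 20 independent visits per type, 30 mph, lognormal round-trip distance (log-SD 0.6), in-person session plus administrative time with mean 90 and SD 20 minutes. Entries are the percentage of runs finding in-person significantly dearer.

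| Median round trip (miles) | Equal time | Telehealth +15 min | Telehealth +30 min |
|---|---|---|---|
| 5 | 68 | 4 | 0 (49 find telehealth dearer) |
| 10 | 99 | 64 | 4 |
| 20 | 100 | 100 | 93 |
| 40 | 100 | 100 | 100 |

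A test of time alone rejects in 4% to 6% of runs with equal time (across 20, 40 and 80 visits per type). With 20 visits per type it rejects in 61% to 64% at +15 minutes and at least 99% at +30. At a 20-mile median, the total-cost result is the same whether telehealth takes equal time or 15 minutes more or less. At 10 miles and +30 minutes, two real differences cancel and the total-cost test sees almost nothing.

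**Step 3. Clustering.** Distance is nearly constant within a dyad, so visits do not supply independent distances. Take a 40-mile median round trip (20 one way), log-SD 0.7, 30 mph and non-travel SD $16. Cost per one-way mile is 2 × 0.67 + 2 × 50/30 = $4.67. Mean one-way distance is 20 × exp(0.245) = 25.6 miles, SD 20.3, so travel has mean $119 and SD $95.

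- 60 independent visits per type: in-person SD = sqrt(95² + 16²) = 96.3; SE = sqrt((96.3² + 16²)/60) = $12.6; statistic 119/12.6, about 9.5; 95% half-width 1.96 × 12.6, about $25.
- About 10 dyads supplying the distances: travel SE = 95/sqrt(10), about $30; statistic about 4; half-width 1.96 × 30, about $59.

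With only 10 independent observations per type, equal times and log-SD 0.7, the test still rejects in about 80%, 98% and 99% of runs at median round trips of 10, 20 and 40 miles. Clustering widens the interval a good deal but does not make the test informative.

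**Step 4. Variance.** Travel's share of in-person cost variance under the Step 3 assumptions is 95²/(95² + 16²) = 97% at a 40-mile median round trip. The same formula gives 90% at 20 miles and 69% at 10.

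**Step 5. Conversion for distance (illustration).** Suppose one home is a 10-mile and one a 40-mile round trip. With equal home visits, mean travel is (23.37 + 93.47)/2 = $58.42. If the near home keeps four visits and the far home one, it is (4 × 23.37 + 93.47)/5 = $37.39.

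**The case against.** The strongest reply is that total organisational cost is the sponsor's question. An organisation pays for travel, the size of the difference is unknown in advance even where its sign is likely, and it is a legitimate budget figure. The plan names a cost difference as primary, reports costs descriptively, states no alpha or decision rule, and calls itself a pilot. It also sets billable minutes against Medi-Cal reimbursement, which is a partial split. All of this stands, and it is why total cost should remain the primary quantity. It does not rescue the zero-difference test, and the reimbursement exercise does not compare administrative time.

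A reader might go further and infer that the primary result is settled by definition, or that the p-value says nothing. The documents do not support that. Session and administrative time enter both visit types and may differ either way. At a 5-mile median round trip, 15 extra telehealth minutes all but remove the difference and 30 can reverse it. That case means a median home 2.5 miles away, which looks unlikely given enrolment at any distance within the state, but actual distances are not given.

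A reader might also infer that session plus administrative time should become the confirmatory comparison. That is not supported either. Actual visit type is not randomised, and complexity or feeding and tone problems, which can move a visit to in-person, may also change how long it takes. A narrow interval for that component could be precise about a confounded contrast.

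**Conclusion.** The concern holds in a limited form. Driving and mileage fix the travel part of the contrast in sign. At assumed median round trips of 20 miles or more, 20 independent visits per type and up to 30 extra telehealth minutes, the total-cost test favours telehealth in 93% to 100% of simulated runs. It cannot show whether session or administrative time differs. The outcome is not predetermined at very short distances, and the size of the total difference remains worth estimating.

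Observed in-person travel cost may also be too low for the enrolled population, because distance is a permitted reason for conversion. The documents do not show how often that happened. Every distance, speed, visit count, visit time and SD used here is an assumption. The weakness lies in how the comparison is summarised and tested, not in measuring total cost.

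**What to change.** Keep total organisational cost per visit as the primary quantity and change its presentation:

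1. Make the mean difference with a 95% confidence interval, clustered by dyad, the headline in place of the p-value.
2. Split it into (a) session plus administrative time cost and (b) drive time plus mileage, with intervals for each.
3. Report (b) as observed in delivered visits, and also standardised: apply the drive time per mile seen in delivered visits, $50 per hour and $0.67 per mile to the recorded home distances of all 20 dyads, then average.
4. Present (a) by actual visit type as descriptive and possibly confounded by the recorded conversion reasons. Put a comparison by assigned group beside it, noting that the assigned groups mix visit types.
5. Give variances by component for planning the later trial.

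The cost is modest: some further analysis of items already recorded, wider clustered intervals, and a modelled travel figure that assumes trips start at the hospital, which the documents do not state. Showing the observed figure beside it keeps that assumption visible.

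### The primary cost outcome is defined as organizational cost but prices therapist time at a bare wage, which understates both visit costs and flatters the comparison with reimbursement

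*Combined protocol and SAP*

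**What the plan says.** Under Implementation outcomes the plan states: "The primary outcome of interest for this study was cost difference between telehealth and in-person visits of the Baby Bridge program". The Cost section that follows sets the perspective: "Cost was defined in relation to the organizational cost of providing Baby Bridge visits". The cost "included the time that the therapist spent conducting therapy sessions (billable time), administrative time (documentation, communication with families", and also "driving (for in-person visits), and mileage reimbursement".

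All of this time is multiplied by $50 per hour, which the text itself calls "an hourly wage that matches typical rates across the United States and in California". Miles are priced at $0.67, "the California mileage reimbursement rate for employees". Billable minutes are then matched to Fee For Service Medi-Cal amounts: "This enabled a total amount of reimbursable potential in context of the total cost of programming". The only caveat given is that reimbursement may vary by insurer; the cost side has none.

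Neither the Cost section nor any other part of the document mentions payroll taxes, benefits or overhead, or a telehealth platform, device or connection. The Cost paragraph under Analysis plans description, t-tests and linear regression by visit type, with no sensitivity analysis on unit prices.

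**The concern.** The plan names one perspective and prices from another. A wage is what the therapist receives. An organization that employs the therapist also pays payroll taxes and benefits on each hour, and the use of an employee mileage rate indicates that the therapist is costed as an employee. Every session, administrative and driving minute is then priced below what it costs the organization.

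Two results are exposed. The first is the cost of each visit type and its comparison with reimbursement, where the error always runs in the favourable direction. The second is the primary difference. The labour error does not cancel there, because driving time is priced only for in-person visits. The component list is also uneven: it has entries specific to in-person visits and none specific to telehealth. If the organization did incur a telehealth cost, leaving it out would push the difference the other way.

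**Working it through.** The plan states no per-visit cost, so there is no figure of its own to reproduce. The check writes its costing rule as arithmetic and varies the unit prices.

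**Inputs from the documents.** $50 per hour and $0.67 per mile (Cost, under Implementation outcomes). A one-hour in-person session: "attempts were made to see the infant weekly in the home environment for a one-hour therapy session" (In-person group assignment).

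**Assumed inputs, not in the documents.** A 60-minute telehealth session, 20 minutes of administration in both modes, a 60-minute drive, 40 miles, labour loading L from 1.2 to 1.5 times wage, and telehealth-specific cost T from $1 to $10 per visit.

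**Formulas** (times in hours)

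- Telehealth = 50 × L × (session + administration) + T
- In-person = 50 × L × (session + administration + drive) + 0.67 × miles
- Difference, with equal session and administrative time in both modes = 50 × L × drive + 0.67 × miles − T
- Change from the planned difference = 50 × (L − 1) × drive − T

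**Rule as written (L = 1, T = 0)**

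- Telehealth: 80/60 × 50 = $66.67
- In-person: 140/60 × 50 + 40 × 0.67 = 116.67 + 26.80 = $143.47
- Difference: 50.00 + 26.80 = $76.80

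**With loading**

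| L | Telehealth, T = 0 | In-person | Difference, T = 0 | T = $1 | T = $10 |
|---|---|---|---|---|---|
| 1.0 (plan) | $66.67 | $143.47 | $76.80 | – | – |
| 1.2 | $80.00 | $166.80 | $86.80 | $85.80 | $76.80 |
| 1.3 | $86.67 | $178.47 | $91.80 | $90.80 | $81.80 |
| 1.5 | $100.00 | $201.80 | $101.80 | $100.80 | $91.80 |

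**Reimbursement comparison.** Loading leaves the reimbursed amount unchanged, so the ratio of reimbursement to cost must fall. At T = 0 the telehealth ratio is multiplied by 1/L: 1/1.2 = 0.83 to 1/1.5 = 0.67. The in-person ratio is multiplied by 143.47/166.80 = 0.86 to 143.47/201.80 = 0.71. Any T above zero lowers the telehealth ratio further.

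**Primary difference.** The two effects cancel when T = 50 × (L − 1) × drive hours. With a one-hour drive this is $10 at L = 1.2, $15 at L = 1.3 and $25 at L = 1.5. Over L = 1.2 to 1.5 and T = $1 to $10 the difference runs from $76.80 (0%) to $100.80 (24.00/76.80 = +31%).

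**Wider range.** A second set of assumptions used 30 minutes of administration, drives of 0.5 to 2 hours, 15 to 80 miles, L = 1.0 to 1.5 and T = $0 to $20. The difference then changes by −57% to +36%. Its smallest value is 25 + 10.05 − 20 = $15.05, so in-person remains the dearer mode throughout.

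**The case against.** The strongest reply is that this is a disclosed choice of scope. The plan says its costs are estimates, lists its components and names both unit prices. A typical wage is a transparent and transferable price for a pilot of 20 dyads, and anyone given the hours can apply their own loading. That stands as a point about disclosure. It does not remove the conflict between a wage and an outcome labelled organizational cost, and the plan does not commit to reporting hours and miles separately. Pilot status explains the absence of a power calculation, not the choice of label.

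Three stronger readings are tempting, and the documents do not support them:

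- **That the primary difference is biased in a known direction, or its conclusion overturned.** Loading and telehealth cost act in opposite directions, and neither is given. Within the illustrated ranges they can cancel exactly, and in-person stays dearer in every scenario computed. No effect on the planned t-test or regression is shown.
- **That a telehealth cost was definitely left out.** Nothing in the document says the organization bought a platform, device or connection for these visits. If existing equipment was used, T could be near zero.
- **That a finding of reimbursement covering cost would be reversed.** The plan sets no break-even rule and makes no such statement; it only places reimbursable potential beside cost. No Medi-Cal amount is given. On the illustrative inputs, a telehealth payment between $66.67 and $86.67 would cover the wage-only cost but not the cost at L = 1.3. Whether any actual payment lies there cannot be tested.

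It is also fair that a loading needs one figure that the plan does not list among its data.

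**Conclusion.** The point holds for the price of labour. Measured against the plan's own perspective, both visit-type costs are understated, and the reimbursement comparison is too favourable for any L above 1. On the illustrative inputs the loaded cost exceeds the wage-only cost by 20% to 50% for a telehealth visit and by 16% to 41% for an in-person visit (23.33/143.47 and 58.33/143.47) at L = 1.2 to 1.5, before any T.

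For the primary difference, what can be said is that it is sensitive to two prices the plan does not state, with no fixed net direction and no demonstrated change of conclusion.

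The direction for the visit costs needs only that the employer pays something on top of the wage. The sizes rest on the assumed loading, administrative time, drive time and miles, and on a telehealth session as long as the in-person one. If session or administrative time differs by mode, the loading scales that gap too.

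**What to change.** Recompute cost with therapist time at the employer's loaded rate, that is, the wage multiplied by L from the employer's own fringe rate. Include a per-visit telehealth cost only if the organization incurred one, and otherwise state it as zero. Use the loaded figure for the comparison with Medi-Cal reimbursement, and report the wage-only figure as a sensitivity row.

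If no loaded rate can be obtained, show results over a range of loadings, label the outcome as direct wage and mileage cost, and do not conclude that reimbursement covers cost.

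The minutes and miles are already needed for the planned calculation, so no new participants or visits are required. The price is one fringe-rate figure to obtain, a check on whether any telehealth cost was incurred, and program costs that look less favourable.
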